### **11.1 Analysis of primary endpoint**

The primary endpoint for the study is the presence of objective side effects during immunotherapy which is defined as binary outcome: yes if any grade of objective side effect occurred, no otherwise.

The primary analysis will compare the proportion of objective side effects between the groups using a Mantel-Haensel estimate of the odds ratio stratified by center. A logistic regression model will be used to control for other possible confounders: age, gender, cardiovascular disease, hypertension, chronic bronchial disease or asthma, total IgE, venom-specific IgE, tryptase levels, mastocytosis, skin test reactivity, and study centers.

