## 1. Study synopsis

APPLICANT / COORDINATING INVESTIGATOR	[name], PhD Department of Dermatology Medical University of Graz [name] [name], Austria [contact] Telefax: [contact] E-mail: [contact]
TITLE OF STUDY	The effect of antihypertensive drugs on severity of anaphylaxis and side-effects during venom immunotherapy
SHORT TITLE	EADOAS-Study
POPULATION	Patients with a history of anaphylactic sting reaction
OBJECTIVE(S)	The primary objective of this study is to evaluate whether subjects under antihypertensive treatment with beta-blockers and/or ACE-inhibitors show more side effects during VIT compared to subjects with no antihypertensive treatment.
INTERVENTION(S)	Venom immunotherapy (VIT)
KEY INCLUSION AND EXCLUSION CRITERIA	Inclusion criteria: Subjects aged from 35 to 85 years with a history of anaphylactic sting reaction  Exclusion criteria (only for phase 2): Absolute contraindications for VIT, Pretreatment with Omalizumab
OUTCOME(S)	Proportion of side-effects during venom immunotherapy
STUDY TYPE	Prospective multicenter observational study
STATISTICAL ANALYSIS	The primary analysis will compare the proportion of objective side effects between the groups (subjects under antihypertensive treatment vs. subjects without antihypertensive treatment) using a Mantel-Haensel estimate of the odds ratio stratified by clinic.  A logistic regression model will be used to control for other possible confounders
ETHICAL APPROVALS	Participating study centers have to obtain ethical approvals from their institutional review boards.
SPONSORING	Unrestricted grants from pharmaceutical companies
SAMPLE SIZE	1319
TRIAL DURATION	July 1, 2014 – December 31, 2019 (End of inclusion phase: January 31, 2018)

PARTICIPATING CENTERS	Name	Address	Country
	[name] [name], MD, PhD	Department of Dermatology Medical University of Graz [name] [name], Austria	Austria
	[name], MD	Clinical Department of Dermatology Medical University of Innsbruck [name] [name], Austria	Austria
	[name]	Department of Dermatology SALK Paracelsus Medical University Salzburg [name] [name], Austria	Austria
	Prim. Univ.-Doz. [name]	Department of Dermatology Elisabethinen Hospital Linz [name] [name], Austria	Austria

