### 5.2 Secondary objectives

- To evaluate whether subjects under antihypertensive treatment with beta-blockers and/or ACE-inhibitors have more severe sting reactions.
- To correlate the prevalence of cardiovascular diseases and/or hypertension with the risk for more severe systemic sting reactions and with more severe and more frequent side effects under VIT.
- To evaluate whether bee venom is associated with a higher frequency of side-effects.
- To evaluate whether high sIgE levels are correlated to a higher frequency of side-effects.
- To evaluate whether high tryptase levels are correlated to a higher frequency of side-effects.
- To evaluate whether quicker up-dosing protocols are correlated to a higher frequency of side-effects.
- To evaluate efficacy of VIT by sting challenges or field stings and look for differences between patients with and without antihypertensive treatment

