### 6.4.5 Venom immunotherapy (VIT)

There is no standard buildup phase; centers use their own standard protocols. Typically, conventional (outpatient), Cluster/Ultrarush- (partial inpatient) and Rush-protocols (inpatient) will be performed. The respective venom that is used for VIT will be recorded (bee or wasp venom, trade name, company). Injections will be administered subcutaneously in the dorsal part of the upper arm, one hand's breadth above the elbow, or in the volar part of the thigh. All interventions will be performed according to the in-house protocols of participating centers.

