### ***Phase 2 (up-dosing of VIT) – Visit 2. (0-4 weeks after reaching maintenance dose)***

- Re-collect medical history, recording of co-medication
- Record of up-dosing scheme and of the respective venom used for VIT
- Record pre-treatment during VIT
- Record of side-effects during VIT up-dosing

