### **11.2 Analysis of secondary endpoints**

For the analysis of secondary endpoints, comparison between groups will be made by using  $\chi^2$  statistics or the Fisher exact test for categorical variables and by t-test or the Mann-Whitney U test for continuous variables.

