**13.2 Table 2**

Study procedures	Visit 1	Visit 2	Visit 3/3a	Visit 3b/c a
	Screening/Inclusion	Up-dosing	Maintenance Phase	Field sting / sting challenge
Informed consent	X			
Inclusion/Exclusion review	X			
Allergy history	X			
Medical history / co-medication	X	X	X	X
Demographics	X			
Collect results of IDT and CAP	X			
Recording of decision regarding venom immunotherapy (yes/no)	X			
Recording of venom used for VIT		X		
Recording of side-effects		X	X	
Recording of stinging insect				X
Recording of sting reaction				X

a if applicable.

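### Section 11.1 adjusts the antihypertensive effect for neither bee nor wasp venom, although the venom is recorded and is itself a suspected cause of side effects

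*Combined protocol and SAP*

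**What the plan says.** Section 11.1 estimates the primary comparison "using a Mantel-Haensel estimate of the odds ratio stratified by center"; the synopsis has the same analysis "using a Mantel-Haensel estimate of the odds ratio stratified by clinic". A logistic model then controls for "age, gender, cardiovascular disease, hypertension, chronic bronchial disease or asthma, total IgE, venom-specific IgE, tryptase levels, mastocytosis, skin test reactivity, and study centers". Venom-specific IgE is on that list; the venom actually injected is not.

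The venom is available for analysis. Section 6.4.5 records it as bee or wasp with the product, section 8 lists for Visit 2 "Record of up-dosing scheme and of the respective venom used for VIT", and Table 2 has a row "Recording of venom used for VIT".

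Section 5.2 includes the objective "To evaluate whether bee venom is associated with a higher frequency of side-effects". Section 11.2 opens "For the analysis of secondary endpoints, comparison between groups will be made by using" and then names only unadjusted tests (chi-squared or Fisher exact, t or Mann-Whitney).

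**The concern.** Section 5.2 names several suspected predictors of side effects. Section 11.1 adjusts for the other patient-level ones (sIgE, tryptase, cardiovascular disease, hypertension) but not for venom. The study is observational and section 7 leaves treatment decisions to routine care, so nothing in the design balances venom between patients with and without antihypertensives.

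Center strata remove venom differences between centers, not within them. One conceivable route to a within-center difference, for which the documents give no data, joins two statements. Section 3.2.3 reports that guidelines favor replacing ACE inhibitors where feasible, and section 11 analyzes only patients who complete buildup. If replacement or completion depended on the venom, the venom mix would differ by group.

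Both planned odds ratios would then carry part of the venom effect. That could produce a false signal or mask a real one, in a study that section 4 expects to settle the question.

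**Working it through.** **Inputs from section 11.3:** 6% vs 12.3% side effects, OR 2.2, groups of 631 and 200, two-sided 5%, 80% power. All venom shares, venom effects and center counts below are assumptions.

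**1. The plan's own figures reproduce.** (0.123/0.877)/(0.06/0.94) = 2.197. The pooled-variance two-proportion formula without continuity correction gives 632 + 201 = 833 against 831 stated, and power at 631/200 is 79.96%. Dropout is 1 − 0.70 × 0.90 = 0.37, and 831/0.63 = 1319. Expected events: 631 × 0.06 + 200 × 0.123 ≈ 62. None of this is affected by the point at issue.

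**2. Closed form, no drug effect.** Let q1 and q0 be the bee-venom shares in the exposed and unexposed groups, and RR the bee-venom risk ratio. The exposed rate is 6% × (1 + q1(RR − 1))/(1 + q0(RR − 1)).

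| q1 / q0 | RR | Exposed rate | Apparent OR | Type I error |
|---|---|---|---|---|
| 25% / 20% | 2 | 6% × 1.25/1.20 = 6.25% | 1.04 | 5.4% |
| 30% / 20% | 3 | 6% × 1.60/1.40 = 6.86% | 1.15 | 8.0% |
| 40% / 20% | 3 | 6% × 1.80/1.40 = 7.71% | 1.31 | 15.4% |

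A second parameterization used venom odds ratios of 2 to 5. With equal bee shares, a null OR stays at 1.00 and a true OR of 2.2 becomes 2.11 to 2.18. With a 10-point difference in bee share, a null OR becomes 0.82 to 1.18 and an OR of 2.2 becomes 1.74 to 2.50.

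**3. Simulated Mantel-Haenszel analysis.** 831 patients, 200 exposed, equal centers, baseline risk spread over 3% to 9%, venom share set within center, Wald test with Robins-Breslow-Greenland variance, 6,000 trials per setting. RR is 3 unless stated. Entries are median OR and rejection rate.

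| Setting | By center (planned) | By center and venom |
|---|---|---|
| Null, 25/20%, RR 2, 4 centers | 1.04, 4.9% | 0.99, 4.6% |
| Null, 30/20%, 4 centers | 1.14, 7.6% | 0.99, 4.7% |
| Null, 40/20%, 4 centers | 1.30, 14.7% | 0.99, 4.4% |
| Null, 40/20%, 20 centers | 1.30, 14.5% | 1.00, 4.5% |
| OR 2.2, 10/20%, 4 centers | 1.83, 55.3% | 2.20, 72.9% |
| OR 2.2, 20/20%, 4 centers | 2.15, 76.4% | 2.20, 77.5% |
| OR 2.2, 20/20%, 20 centers | 2.14, 76.2% | 2.20, 76.0% |

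A repeat of the balanced case gave 75.5% vs 77.2% power with 4 centers and 76.0% vs 74.3% with 20.

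**4. Simulated logistic model.** 1,500 trials, the listed covariates plus centers, null drug effect, 40/20% bee venom. The planned model gives OR 1.30 if venom-specific IgE carries no venom information, and 1.26 or 1.15 if IgE is shifted by 1 or 2 SD in bee-venom patients. Adding venom gives 0.98 to 0.99.

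**The case against.** The strongest reply is that confounding has not been shown. A confounder must relate to exposure as well as outcome. The documents raise bee venom only as a question about outcome, and no passage ties venom to beta-blocker or ACE-inhibitor use. This stands: venom is a suspected predictor, not an established confounder, and no document figure places the trial within the assumed range. But section 11.1 calls its own covariates possible confounders, so proof of imbalance is not the plan's standard for inclusion.

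Second, the logistic model already holds markers of venom. Section 6.4.3 measures IgE to bee and vespid venom separately, and skin test reactivity is listed. In a simplified simulation of the 40/20% null case, the OR fell from 1.30 with no marker to 1.09 when the two IgE values entered separately with opposite 2 SD shifts. It fell to 1.04 with two similar skin-test markers added, and was 1.14 with four markers shifted by only 1 SD. So the bias in the logistic model may be well below 1.30. These shifts are assumptions too, section 11.1 does not say that IgE enters by venom, and none of this helps the primary Mantel-Haenszel estimate.

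Third, section 11 promises percentages for categorical variables, which could include venom by group. It does not name venom, and it does not promise the split within center, which is what matters here.

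Finally, the up-dosing scheme is likewise recorded, named in section 5.2 and absent from the list. That is a parallel gap; it does not excuse this one.

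**Conclusion.** The concern holds. As written, no planned analysis of the antihypertensive effect adjusts for the venom used. The consequence is conditional: none if venom is balanced or differs only between centers, negligible for a small within-center imbalance, and material only if a sizeable imbalance meets a strong bee-venom effect. Size and direction cannot be determined from the documents, and the planned report need not show which case applies. This is a recommended improvement, held with medium confidence; it is not a flaw that invalidates the primary analysis.

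**What to change.** Keep the center-stratified Mantel-Haenszel odds ratio as primary. It had clearly more power in simulation than the full logistic model (about 76% vs 53% at OR 2.2 with balanced venom). In section 11.1:

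1. Add to the logistic covariates: *venom used for VIT (any bee venom vs wasp venom only)*.
2. Add: *As a sensitivity analysis, the Mantel-Haenszel odds ratio stratified by center and venom will be reported with its 95% CI beside the primary estimate; the primary conclusion rests on the center-stratified estimate.*
3. Add: *Venom used for VIT will be tabulated by antihypertensive group within center.*

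The change is to wording only; the data are already collected and the sample size stands. The costs are one more logistic parameter (standard error of the log odds ratio up 0% to 4% in simulation) and sparser strata in the sensitivity analysis. With balanced venom, that analysis had a standard error of 0.286 against 0.280 with 4 centers (up 2%) and 0.297 against 0.283 with 20 (up 5%); the increase was at most 6% with imbalance. With 20 centers and 10% vs 20% bee venom, 5.6% of patients fell in strata holding only one group and did not contribute. The center list available for this review is incomplete, so the true number of centers, and with it the sparsity, is not known here.

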### **11.2 Analysis of secondary endpoints**

For the analysis of secondary endpoints, comparison between groups will be made by using  $\chi^2$  statistics or the Fisher exact test for categorical variables and by t-test or the Mann-Whitney U test for continuous variables.

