### 3.1.2 Potential effect on immunotherapy

- *Side effects do not appear to be more frequent, but maybe more serious*
- *Side effects could be refractory to treatment*
- *Emergency treatment may cause paradoxical treatment effects*

Both beta blockers and allergen immunotherapy are frequently prescribed, therefore allergists commonly encounter patients who are candidates for immunotherapy and are treated with beta blockers. Fatality studies have shown that particularly elderly patients with pre-existing cardiovascular disease die from hymenoptera venom allergy. Therefore unlike for respiratory allergies, immunotherapy with hymenoptera venoms is commonly performed in elderly patients who are more likely to be on beta blocker treatment.

The risk of beta blocker treatment is still questionable. There is plenty of experimental human and animal studies mainly performed in the 1970s and 80s as well as anecdotal clinical evidence that anaphylaxis may be influenced by pharmacodynamics of  $\beta$ -blockade. In theory,  $\beta$ -blockade perturbs the control of endogenously produced mediators of anaphylaxis resulting in an enhanced generation, release, and reduced effects of these mediators on the end organs. If anaphylaxis occurs in a patient on beta-blocker, it may therefore be more severe and protracted. There is also evidence that even beta-blocker eye drops have systemic effects. However, the plurality of uncontrolled variables makes the susceptibility of individual patients to this effect of topically and orally applied beta-blockers largely unpredictable. The second point is that emergency treatment with epinephrine may be ineffective or promote undesired  $\alpha$ -adrenergic and vagotonic effects.  $\beta$ -blockade dramatically alters pharmacotherapeutic actions of epinephrine and isoproterenol, as up to 80-fold higher doses may be necessary. Additionally, the block of  $\beta_1$  and  $\beta_2$  actions of epinephrine may facilitate unopposed  $\alpha$ -adrenergic and reflex vagonotonic effects, which can result in increased mediator release, bronchoconstriction and bradycardia. The pronounced  $\alpha$ -receptor activation in the presence of epinephrine may also constrict coronary arteries or exaggerate systemic pressor effects of epinephrine leading to severe hypertensive episodes.

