There are three clinical studies dealing with the question whether patients taking beta-blockers are at increased risk of having side effects during immunotherapy. Hepner et al prospectively studied 3178 patients; 68 patients were taking beta-blockers. Although statistically 3 patients were expected to have systemic reactions, only one patient taking a beta-blocker had a systemic reaction. In a retrospective study of Mueller et al, 1389 patients were included, and 25 patients were on beta-blockers during immunotherapy. They also did not find an increased incidence of systemic reactions, and reactions were not more severe than in the control group. Most recently, an EAACI observational prospective multicenter study on 680 patients (15 on beta-blockers) could not identify beta-blocker therapy as independent predictor for an emergency intervention during immunotherapy. Interestingly, in a former EAACI observational study on 962 patients (52 on beta-blockers) beta blocker were not identified as independent risk factor for severe anaphylaxis, which

was consistent with a large Australian study. In this study, case records of 1149 patients were retrospectively analyzed. Univariate analyses suggested that reaction severity was influenced by beta-blockers. However, in the multivariate analysis beta-blockers were not identified as independent risk factor. Recently, 657 patients suitable for VIT were included in a large single-center observational study. 59 were on beta-blocker treatment; 27 on both, ACE-inhibitors and beta blockers. Again, beta blockers were not identified to be correlated with severe anaphylaxis. More recently, again controversial data have been published: Beta-blockers were not associated with severe anaphylactic symptoms such as syncope or hypotension, but with 3 or more organ involvement and hospitalization.

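### Section 11.2 plans only unadjusted tests for sting-reaction severity by antihypertensive group, so a plausible confounding bias of unknown size is left uncontrolled

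*Combined protocol and SAP*

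**What the plan says.** Section 7 describes an open, prospective observational study, so antihypertensive use is not randomised. Section 5.2 opens with "To evaluate whether subjects under antihypertensive treatment with beta-blockers and/or ACE-inhibitors have more severe sting reactions" and closes with "To evaluate efficacy of VIT by sting challenges or field stings and look for differences between patients with and without antihypertensive treatment". Both are comparisons between the two drug groups.

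Section 11.2 is a single sentence. It compares groups on secondary endpoints by chi-square "or the Fisher exact test for categorical variables and by t-test or the Mann-Whitney U test for continuous variables". It names no covariates and no stratification.

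The adjusted model appears in Section 11.1, under the primary endpoint: "A logistic regression model will be used to control for other possible confounders: age, gender, cardiovascular disease, hypertension", followed by further covariates that include tryptase and center. Its outcome is objective side effects during immunotherapy. The synopsis mentions the model directly after the primary analysis and names no secondary endpoint.

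The background in Section 3.1.2 bears on confounding in three places:

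- On exposure: "immunotherapy with hymenoptera venoms is commonly performed in elderly patients who are more likely to be on beta blocker treatment".
- On outcome: "particularly elderly patients with pre-existing cardiovascular disease die from hymenoptera venom allergy".
- On an earlier retrospective study of 1149 case records: "Univariate analyses suggested that reaction severity was influenced by beta-blockers". The protocol adds that the multivariate analysis did not confirm this as an independent effect.

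Section 5.2 also treats cardiovascular disease and hypertension as possible severity factors in their own right: "To correlate the prevalence of cardiovascular diseases and/or hypertension with the risk for more severe systemic sting reactions".

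**The concern.** If drug users are older or have more cardiovascular disease, and these factors raise severity, a crude comparison can show a drug association when the drugs do nothing. Section 11.1 accepts the need to adjust when the outcome is side effects. Section 11.2 does not carry it over to severity.

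The question is prominent. Severity of anaphylaxis comes first in the study title, and Section 4 expects the data to support a clear conclusion on the risk of these drugs. A crude association could easily be read as a drug effect. Without a prespecified model, the choice between crude and adjusted results would also be made after seeing the data.

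**Working it through.** **The plan's own figure.** Section 11.3 gives the only design calculation, for side effects: 6% against 12.3% with 631 and 200 patients.

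- Odds ratio: (0.123/0.877)/(0.06/0.94) = 2.197.
- Pooled rate: (37.86 + 24.6)/831 = 0.0752. Null SE: √[0.0752 × 0.9248 × (1/631 + 1/200)] = 0.0214. Alternative SE: √[0.06 × 0.94/631 + 0.123 × 0.877/200] = 0.0251.
- Power: Φ[(0.063 − 1.96 × 0.0214)/0.0251] ≈ 0.80, as stated.
- Dropout: 1 − 0.7 × 0.9 = 0.37, and 831/0.63 = 1319.05, against 1319 stated.

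The design reproduces, but it says nothing about severity. The documents give no severity rate, no confounder distribution by group and no confounder–severity association. Everything below is therefore illustration. Only the 831, 631 and 200 come from the plan; Section 11 bases the analyses on patients who complete the buildup phase.

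**Assumed inputs.** No drug effect. Mean age 58.5 in users and 54.1 in non-users, with age odds ratio 1.2 per 10 years. Hypertension in 70 to 90% of users against 20 to 10% of non-users. Cardiovascular disease in 35% against 7%. Each disease has a severity odds ratio of either 1.0 or 1.5. Tryptase affects severity but is unrelated to drug use. Severe means grade III or higher in Table 1A, in 8 to 20% of patients.

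**Bias, by hand.** To a good approximation, ln(crude OR) ≈ Σ (difference in confounder mean) × ln(confounder OR).

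- Age: 0.44 × ln 1.2 = 0.080.
- Both diseases at 1.0: exp(0.080) = 1.08.
- Both at 1.5, weaker overlap: 0.080 + (0.50 + 0.28) × 0.4055 = 0.397, OR 1.49.
- Both at 1.5, stronger overlap: 0.080 + (0.80 + 0.28) × 0.4055 = 0.518, OR 1.68.

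Simulation (2000 runs per setting) gives 1.07–1.08 and 1.46–1.68.

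**Rejection by the crude test.** SE ≈ √[(1/200 + 1/631)/(p(1 − p))], with p the severe share. This is 0.203 at 20%, 0.216 at 17%, 0.271 at 10% and 0.299 at 8%.

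- Diseases at 1.0: 0.080/0.216 and 0.080/0.299 give about 6 to 7% two-sided. Simulations give about 4 to 7%.
- Diseases at 1.5: from 0.397/0.271 (31%) to 0.518/0.203 (72%). Simulation gives about 35 to 75%.

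The adjusted model gives odds ratios of 0.98–1.01 and rejects in 4.3–5.9% of runs. That is expected, because it contains every simulated confounder.

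**Cost in precision.** The simulated standard error of the drug effect is 22 to 63% larger after adjustment. The odds ratio detectable with 80% power is exp(2.802 × SE).

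| Severe share | Disease OR | Crude, by hand | Adjusted, by hand (SE × 1.22 to 1.63) | Simulated |
|---|---|---|---|---|
| 20% | 1.5 | 1.77 | 2.00–2.53 | 1.7 to 2.0–2.4 |
| 17% | 1.0 | 1.83 | 2.09–2.68 | 1.8 to 2.1–2.7 |
| 10% | 1.5 | 2.13 | 2.52–3.44 | 2.0 to 2.4–3.2 |
| 8% | 1.0 | 2.31 | 2.78–3.92 | 2.3 to 2.7–3.8 |

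The cost is largest where the bias is smallest.

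**Events per parameter.** Drug group, age, sex, cardiovascular disease, hypertension, tryptase and three center terms (four centers visible in the synopsis) make nine parameters. If 10% are severe, 83.1/9 = 9.2; if 20%, 166.2/9 = 18.5. These are upper limits, because the visible center list may be incomplete and each further center adds a term.

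**The case against.** **The synopsis sentence is not limited to the primary endpoint.** True, but it follows the primary analysis of side effects, and Section 11.1 places the model under the primary endpoint. If adjustment of severity was intended, 11.2 should say so.

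**The background evidence is soft.** This stands. The link with age and cardiovascular disease concerns deaths, not Table 1A grade among living enrolled patients. In the earlier study, loss of independence in a multivariate model can reflect lost precision as well as confounding, and its covariates are not shown. A reader might infer that confounding has been demonstrated; the documents support only that it is plausible.

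**The objective may be purely descriptive.** Section 5.2 can be read as asking about a marginal association, and the chi-square test holds its 5% level for that question. A reader might infer an inflated type I error. That is not the point: the risk is confounding bias when the result is read as a drug effect.

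**Adjustment may gain little and cost precision.** This also stands for some inputs. If neither disease affects severity, crude rejection stays near 5% and the adjusted interval is clearly wider.

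**Adjustment cannot repair everything.** Section 6.4.1 records current medication at Visit 1, after the sting. Whether the case report form also captures drug use at the time of the sting cannot be seen. Residual confounding will remain as well.

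**Conclusion.** The gap is real: neither sting severity nor field-sting and sting-challenge outcome by drug group has planned confounder control. It should be fixed, as a cheap improvement to a secondary analysis.

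The size of the bias is open. On the assumed inputs it runs from negligible to a crude odds ratio of about 1.7 with no drug effect, and these inputs do not bound it. Age and cardiovascular disease would plausibly push the crude estimate upward, but other listed factors could act either way, so the direction is not fixed.

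A reader might infer that the severity result will be falsely positive, or that the study's main conclusion is compromised. The documents support neither. The primary analysis has its own adjusted model, and the sample size rests on side effects alone. Nothing here calls for a change to the Section 11.1 model.

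**What to change.** In Section 11.2, prespecify the main drug-group analysis of sting severity as a regression on the Table 1A grade: ordinal, or logistic for grade III or higher if proportional odds does not fit. Adjust for age, sex, cardiovascular disease, hypertension, tryptase and center. Add other Section 11.1 covariates as event numbers allow, and give a reason for any left out. Keep the crude tests as descriptive.

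Apply the same principle to field-sting and sting-challenge outcomes as far as event numbers allow. Estimate the association of cardiovascular disease and hypertension with severity in a separate model that does not condition on drug group, so that coefficients from the drug model are not misread.

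The cost is some plan wording and a small amount of extra modelling. All the covariates are already listed in Section 11.1. History, demographics and tryptase are collected at Visit 1 (Section 8), and centers are coded (Section 12.4). The price is the wider interval shown above. The report should also state that exposure is recorded after the sting and that residual confounding remains.
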